Treatment response: The Clinical Global Impression (CGI)^{98,99} scales are used to rate the severity of illness and assess response to treatment. CGI-Severity scale (CGI-S) is used to assess the severity of illness and CGI – Improvement scale (CGI-I) is used to assess treatment response in psychiatric patients. Both are 7-items scale. The CGI-S ranges from 1= normal to 7 = extremely ill.. The CGI-I rates participants improvement from baseline: 1=very much improved; 7=very much worse.

Primary Efficacy Measures: Changes in HAMD, PHQ9 and BSS;

Statistical Analysis

- a. All subjects will be tracked over the study period in order to capture (1) the number subjects randomized to each group; (2) the number of subjects who drop-out or are lost to follow-up, and (3) the compliance of each subject across the study period.
- b. Baseline balance analyses: At baseline, the two groups (Experimental and Control) will be compared on demographic and clinical features, including medical comorbidity, pain, fatigue and post concussive symptoms.
- c. Effectiveness analyses: Random effects models will be used to evaluate the efficacy of the intervention as assessed by HAMD and PHQ9 with comparison of the slopes of the rTMS (Experimental) and sham treatment groups (Control). Random effects models will also be used to compare the two groups over time, controlling for baseline variables found to be statistically significant between the two groups, and the coefficient of interest, such as the interaction between time and treatment assignment. Similar analysis will be done for the CGI-I and BSS scores.

In addition, remission rates (as defined by HAMD score ≤ 7 or PHQ9 = 0) and Improvement rates (as defined by CGI-I scores ≤ 2) between the two groups will be calculated using Fischer's Exact test.

Secondary Objective: To determine the effectiveness of LFR rTMS for the treatment of common co-morbid neuropsychiatric symptoms: (a) Post traumatic stress disorder (PTSD) (b) Sleep disturbance and (c) Cognitive deficits.

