Neuropsychological Tests: All subjects will complete neuropsychological testing at two time points: during the baseline visit and at the 3-month follow-up visit. The test battery will be constructed to allow evaluation of multiple domains of cognitive functioning, including global cognitive functioning, executive functioning, attention, and memory (Table 6). Briefly, the raw scores on all cognitive measures will be converted to scaled scores using the cumulative frequency distribution of each measure. Scaled scores will then be regressed on age, gender, race, years of education, and estimated premorbid IQ based on the revised National Adult Reading Test (NART)^{105,106} . No additional control for education is necessary.

Table 6: Neuropsychological Tests

Montreal Cognitive Assessment	Test of global cognitive functioning
Wechsler Test of Adult Reading (WTAR)	Pre-morbid Intelligence
Trails B	Test of Executive functioning
Controlled Oral Word Association Test (COWAT)	Test of Executive functioning
Wisconsin Card Sorting test (WCST)	Test of Executive Functioning
Stroop Test	Test of Executive Functioning
Brief test of Attention (BTA)	Test of auditory attention
Trails A	Test of visual attention
Hopkins Verbal learning test (HVLT)	Verbal Memory Test
Brief Visual Memory Test (BVMT)	Visual Memory Test

Behavior Problems: The Neurobehavioral Rating Scale—Revised (NBRs-R) will be used to measure behavioral disturbances following TBI. The NBRs-R is a clinician-based multidimensional instrument and has been validated as a secondary outcome measure to assess behavior problems after brain injury¹⁰⁷.

Secondary Efficacy Measures: DTS; PSQI, EPS, PSG and cognitive measures.

Statistical Analysis: Analyses will be similar to Aim1. Random effects model will be used to compare of the slopes of the LFR rTMS (Experimental group) versus the sham treatment group (Control group) on the Davidson Trauma Scale scores. Random effects models will also be used to compare the two groups over time, controlling for baseline variables found to be statistically significant between the two groups, and the coefficients of interest, such as the interaction between time and treatment assignment.

This same statistical analysis approach will be used to compare the two groups on the sleep scales (PSQI & EPS) and on the primary PSG sleep variables, global cognitive functioning and memory, attention and executive functioning.

Exploratory Analyses:

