DTI data will be acquired with a single-shot, echo-planar imaging (EPI) sequence with sensitivity encoding (SENSE), using a parallel-imaging factor of 2.5. The imaging matrix is 96 X 96 with a field-of-view of 212 X 212 mm (nominal resolution, 2.2 mm), zero-filled to 256 X 256 pixels. Transverse sections of 2.2 mm thickness will be acquired parallel to the anterior commissure-posterior commissure line. A total of 60-65 sections will cover the entire hemisphere and brainstem without gaps. Diffusion-weighted images at $b = 700$ s/mm² along 32 directions will be acquired in addition to five additional images with minimal diffusion weighting ($b \approx 33$ mm²/sec). The scanning time per dataset will be approximately 4 minutes. To enhance the signal-to-noise ratio, this procedure will be repeated 3 times. From this, fractional anisotropy (FA) and mean diffusivity (MD), and eigenvalues will be calculated. In this proposal, we will perform hypothesis-based regional analysis of the DTI-derived parameters using manual regions of interest (ROI). ROI will include frontal and temporal regions, the fornix, cingulate, anterior limb of the internal capsule, genu and splenium corpus callosum. We will also perform whole-brain analyses using a brain normalization technique developed in [name] lab¹⁰⁸. Combination of the two approaches (manual regional and automated whole brain analyses) will ensure the robustness and regional specificity of the ROI-based findings.

Other Scales: Other scales described below will be used to assess medical comorbidity, pain, fatigue and postconcussive symptoms all of which can confound the results and will be controlled in the different regression analyses.

Medical Co-morbidity: The General Medical Health Rating (GMHR)¹⁰⁹ will be used to assess overall medical co-morbidity. The scale is simple to use and provides a rating of overall general medical health taking into consideration all medical problems and medications. The scores on this scale ranges from 1 (poor; unstable medical health) to 4 (stable; excellent health). The PI has used this scale previously in her TBI studies.

Pain: The SF-36 bodily pain scale¹¹⁰ will be used to assess pain. It has been found to be a valid measure of pain assessment.

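### The adjusted models choose covariates by baseline significance tests, and no model names the outcome's baseline score or the stratification factor

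*Combined protocol and SAP*

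**What the plan says.** Under the primary objective in Section 6, Statistical Analysis item b has the arms "compared on demographic and clinical features, including medical comorbidity, pain, fatigue and post concussive symptoms". Item c then plans two random effects analyses of HAMD and PHQ9. The first compares slopes and names no covariates. The second compares the groups over time, "controlling for baseline variables found to be statistically significant between the two groups", and describes its target as "the coefficient of interest, such as the interaction between time and treatment assignment". CGI-I and BSS are to be handled in a similar way. Neither analysis is ranked above the other.

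The secondary objective repeats the rule for the Davidson Trauma Scale and extends it: "This same statistical analysis approach will be used to compare the two groups on the sleep scales", and also on the polysomnogram and cognitive measures.

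Two other places speak of covariates. Under Other Scales, medical comorbidity, pain, fatigue and post-concussive symptoms are described as factors "all of which can confound the results and will be controlled in the different regression analyses". Under Neuropsychological Tests, "Scaled scores will then be regressed on age, gender, race, years of education, and estimated premorbid IQ", followed by "No additional control for education is necessary".

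Study Design (Section 4) stratifies randomisation on time since injury, below five years against five years or more. That factor appears in no model. The role of the baseline score is not stated either. The references to slopes, to changes in the primary measures and to five visits including baseline suggest that it is a response. CGI-I has no baseline value: "The CGI-I rates participants improvement from baseline".

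**The concern.** After proper randomisation, any baseline difference between arms arises by chance. A significance test of that difference says nothing about whether the variable predicts outcome, so a strong predictor that happens to be balanced is left out and an irrelevant variable that happens to be unbalanced is put in. The content of the adjusted model then depends on the data, and with 30 participants each covariate uses up information. The variable most likely to predict a depression score is its own baseline value, and the plan does not say how that value is used. The stratification factor, which the design treats as important, is also missing from the analysis.

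At stake are precision in a small trial and a clear answer to which adjusted model will be fitted.

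**Working it through.** The documents give no SD, no correlation between visits and no standardised effect for these scales. The effect sizes (0.8 or 1.0 SD) and correlations r below are assumptions. The arms are 15 and 15, and tests are two-sided at 0.05 (Section 6, General Description).

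**1. The plan's own figure.** Table 7, first row (0.7 against 0.1, power 0.9): [1.960·√(2·0.4·0.6) + 1.282·√(0.21 + 0.09)]² / 0.6² = 11.8 per arm. With the continuity correction, (11.8/4)·[1 + √(1 + 4/(11.8·0.6))]² = 14.9, so 15. All ten rows reproduce in this way. The table compares two unadjusted proportions, so the covariate rule does not touch it.

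**2. Chance that the rule selects something.** Named candidates: seven demographic (age, gender, education, vocational status, living situation, income, marital status), three injury or legal (cause of trauma, litigation, TBI severity) and four scales, 14 in all. The lists are open-ended.
- Independent, each test of size 0.05: 1 − 0.95¹⁴ = 0.51, with 14 × 0.05 = 0.7 selected on average.
- Seven binary, tested by Fisher's exact test: its true size at 15 per arm is 0.0055 at 10% prevalence and about 0.016 to 0.017 at 20 to 50%. Then 1 − 0.95⁷·(1 − size)⁷ = 0.33 to 0.38.
- All continuous and equally correlated at 0.2, 0.3 or 0.5: about 48%, 45% and 36% by simulation, good to about a point.
- A continuous variable is selected only if the observed imbalance reaches 2.048·√(2/15) = 0.75 SD.

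**3. HAMD, PHQ9 and BSS: effect of the rule.** In complete data, a baseline covariate entered as a main effect does not change a time-by-treatment estimate, which is a within-person contrast. Simulated over five visits with a sustained 0.8 SD effect and baseline as a response, power with and without the rule is 0.784 and 0.784 at r = 0.5, and 0.946 and 0.947 at r = 0.7. With 5% dropout per visit the estimate moves by 0.002 SD on average, and the significance call changes in under 0.3% of trials.

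**4. HAMD, PHQ9 and BSS: effect of not conditioning on baseline.** At end of treatment, leaving baseline means free by arm amounts to a change score with variance V = 2(1 − r). Conditioning gives V = (1 − r²)(1 + 1/26), where 1/26 is the expected price of chance imbalance. The noncentrality is 0.8/√(2V/15), with 28 and 27 degrees of freedom.

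| r | V, change | noncentrality | power | V, conditioned | noncentrality | power |
|---|---|---|---|---|---|---|
| 0.3 | 1.40 | 1.85 | 0.43 | 0.945 | 2.25 | 0.58 |
| 0.5 | 1.00 | 2.19 | 0.56 | 0.779 | 2.48 | 0.67 |
| 0.7 | 0.60 | 2.83 | 0.78 | 0.530 | 3.01 | 0.83 |

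Keeping baseline as a response also recovers the loss if both arms share one baseline mean. In simulated random-intercept models, end-of-treatment power is about 0.71 (r = 0.5) and 0.86 (r = 0.7) with a common mean, against 0.59 and 0.80 with free means.

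**5. CGI-I.** If a treatment main effect or visit-averaged difference is tested, the selected covariates act on it directly. Simulated as a single post-baseline score, power falls from 0.560–0.568 to 0.507–0.524 at 0.8 SD, and from 0.757–0.760 to 0.699–0.719 at 1.0 SD. The call changes in 6 to 10% of trials. With no effect, the rule alone rejects in 4.6 to 5.0% of trials, and success on either the unadjusted or the adjusted model in 5.7 to 6.3%. If the time-by-treatment term is tested in complete data, none of this applies, for the reason in step 3.

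**6. Stratum.** With an assumed stratum effect of 0.5 SD, adding it moves simulated ANCOVA power from 0.839 to 0.846.

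**7. Cognitive scores.** Age, gender and education are in the norming regression and are also candidates under the rule. The chance that at least one enters again is 11% (gender tested by Fisher) to 14% (1 − 0.95³). If the remark on education keeps it out, this falls to about 7 to 10%.

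**The case against.** The strongest reply is that the rule has almost no consequence where it matters most. The plan's example of a target is the time-by-treatment interaction, and for HAMD, PHQ9 and BSS that term is essentially unaffected. This stands.

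It also stands that the CGI-I loss and the roughly 6% error rate require a main effect or visit-averaged test. The plan offers the interaction only as an example, so such a test is possible, but it is not stated. The CGI-I improvement rate has its own Fisher test, which is unaffected.

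The power loss in step 4 is not a proven feature of the plan. The documents do not say that baseline means are free by arm, and a model with baseline as a response and a common mean loses nothing.

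A reader might infer that Other Scales and Neuropsychological Tests flatly contradict the rule. The text does not carry that far. The passage on the four scales follows the imaging analyses and may refer only to those regressions. The norming regression concerns cognitive scores alone and is no rival covariate set for the depression models.

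Finally, this is a 30-person pilot. That limits the weight of the point but does not defend the rule, since a small trial has the least information to spare.

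**Conclusion.** The point holds in a limited form. The rule is in the plan for both primary and secondary outcomes, it leaves the adjusted model unfixed, and the use of the outcome's baseline score and of the stratum is unspecified. The gain from correcting this depends on what the sponsor means to fit. It is about 5 to 11 points of power at end of treatment for r between 0.7 and 0.5 if baseline is otherwise not conditioned on, and none from that source if a common baseline mean was intended. The stratum adds under one point. These figures rest on an assumed 0.8 SD effect and assumed correlations; the selection probabilities rest on independent candidates unless stated.

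A reader might infer that the rule biases the depression result or inflates its type I error. The documents do not support that: the rule alone stays near 5%. Nor does the point show that the slope comparison should give way to another primary contrast. An end-of-treatment contrast conditioned on baseline has power 0.67 at r = 0.5, against 0.78 for a treatment-by-post-baseline term with baseline as a response, so that change could lower power. No stated figure in the plan is wrong. The change is worth making because it is cheap and settles which model is fitted.

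**What to change.** - Delete the significance rule under both objectives and keep the baseline comparison descriptive.
- State that each random effects model conditions on the outcome's baseline score, either as a covariate with the post-baseline visits as responses, or as a response with one baseline mean common to both arms. Include the time-since-injury stratum.
- For CGI-I, adjust for a baseline severity score: baseline HAMD, or CGI-S if it is confirmed that CGI-S is rated at baseline.
- For polysomnogram and cognitive outcomes, which have one later time point, use ANCOVA on the baseline value. Do not re-enter variables already used in the norming regression.
- Make adjustment for the four Other Scales measures, at their baseline values, a named sensitivity analysis, and say which analyses that paragraph covers.

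The choice among slope, visit average and end of treatment as primary contrast is a separate decision for the sponsor and is not part of this change.

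The cost is SAP wording and one or two degrees of freedom. Baseline outcome measures are already planned in the Study Overview, the HAM-D17 is scored for eligibility, and the stratum is known at randomisation. Only the timing of the CGI-S rating needs to be confirmed.

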Specific Aim 2: To determine the effectiveness of LFR rTMS for the treatment of neuropsychiatric symptoms that are commonly seen as co-morbid phenomena in patients with post-TBI depression: (a) post traumatic stress disorder (PTSD) (b) sleep disturbance and (c) cognitive deficits. We hypothesize that LFR rTMS will be superior to sham treatment in reducing symptoms of PTSD, sleep disturbance and cognitive deficits, more specifically, memory, attention and executive function deficits. In addition, effectiveness of rTMS for the treatment of other behavioral symptoms (e.g. apathy, aggression) will be assessed.

Exploratory Analysis: A subset of subjects will be assessed using diffusion tensor imaging (DTI) to determine white matter integrity pre- and post-treatment in an effort to better understand neuro-anatomical correlates of NPS symptoms, symptom improvement, and the potential for LFR rTMS to influence white matter integrity.

Study Design: The study design will include a double-blind placebo-controlled trial of 30 TBI patients of mild & moderate severities. Subjects will be randomized to either active LFR rTMS (N=15) or sham treatment (N=15). All subjects will receive 20 LFR rTMS or sham treatments over 4 weeks, and will be followed thereafter for 3 months. Well-validated psychiatric instruments and cognitive assessments will be

used to compare the effectiveness of LFR rTMS versus sham treatment cross-sectionally at each of the visits and over time.

Relevance: If the proposed rTMS treatment is found to be efficacious, it can be transferred to clinical practice for soldiers with TBI-associated depression and other psychiatric symptoms. rTMS has minimal long-term side effects and is not known to negatively interact with pharmacotherapies. rTMS has the potential to have a broad impact on multiple areas of life functioning and, thus, has the potential to lead to improved instrumental life activities, employability, community re-integration and overall quality of life. Soldiers & civilians with increased emotional stability and improved cognitive skills can more effectively manage stress which, in turn, can dramatically reduce the likelihood of developing disorders associated with chronic stress.

2. Objectives

The overarching goal of this proposed proof of concept study is to determine the effectiveness of low frequency right (LFR) rTMS for the treatment of post-TBI depression and co-morbid psychiatric symptoms.

SPECIFIC AIMS & HYPOTHESES

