There is no Food and Drug Administration (FDA) approved drug for the treatment of TBI-related NPS symptoms/syndromes. There are only two controlled medication trials in TBI-associated depression, and neither provided strong evidence that antidepressants are superior to placebo. A major limitation of previous studies has been their focus on limited symptoms and use of agents with narrow therapeutic profiles. We propose to address some of these limitations by use of a novel non-invasive technique, LFR rTMS, that has the potential to induce widespread neuromodulation.

Justification and safety information if FDA approved drugs will be administered for non-FDA approved indications or if doses or routes of administration or participant populations are changed. NA

Justification and safety information if non-FDA approved drugs without an IND will be administered. NA. We anticipate that the Johns Hopkins IRB will classify our trial as significant risk, in which case we will require an IDE from the FDA.

6. Study Statistics

General Description

- a. Definition and selection of dataset: Intention-to-treat (ITT) will include all subjects who are randomized to participate in the protocol. The per-protocol (PP) population will include all subjects in the ITT population who meet the additional criteria of no major protocol violations and compliance with study treatment. Baseline demographic and clinical features, including medical comorbidity, pain, fatigue, and post-concussive symptoms will be included in the ITT dataset. Effect assessment will be included in both the ITT and PP dataset.
- b. Basic exploratory analyses will first be conducted, including checking of distributional assumptions, assessment of relationships among covariates, and missing-value multiple imputations.
- c. Continuous variables will be described using means, standard deviations, medians, minimums and maximums, and 95% confidence intervals for parameter estimation. Graphical display (spaghetti plots) of the outcome scores will also be generated for 5 visits (baseline, end of 20 LFR rTMS sessions, week 8,12, and 16) by group. Category and count variables will be described using frequency or proportions.
- d. Analyses will be conducted using STATA 11.2 (StataCorp, Texas, 2009) or R 2.13.2 (2011). All statistical tests will be judged for significance based upon a two-sided p-value of less than 0.05.

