Fatigue: The Fatigue Severity Scale¹¹¹ will be used to assess the severity of fatigue. It has been used both clinically and for research applications, and has been used in the assessment of fatigue in neurological and non-neurological conditions.

Post-Concussive Symptoms: As a myriad of post-concussive symptoms are present after TBI, the Rivermead Postconcussive Questionnaire¹¹² will be used to determine post-concussive symptoms and calculate the total score.

Power Analysis:

The power calculation for this study is based on the study by Fann et al⁴⁵ and our clinical experience. In the open labeled study of sertraline (Zoloft) for the treatment of TBI depression, Fann et al found a response rate (decrease in Hamilton depression scale score of > or = 50%) of 87% and remission rate (Hamilton depression scale score of < or = 7 at the end of treatment) of 67%. Based on these results, we hypothesize improvement in symptoms on the HAMD of 60-70% in the experimental group; and based on our clinical experience, we hypothesize a remission rate of 10% in the Control group. The table (Table 7) below depicts sample sizes for these remission rates with various degrees of power. As this is a pilot study, we have chosen a sample size (N=30) that is feasible and that will allow us to complete the study in the allocated time. Results from this study will help us to develop future studies with larger sample sizes and more conservative numbers. Sample size was calculated with (StataCorp, Texas, 2009) alpha was set at 0.05.

Table 7: Calculation of Sample Size.

Power	Remission rate in Experimental group (control group is 0.1)	N1 (Experimental group)	N2 (control group)	N (total)
0.9	0.7	15	15	30
0.8	0.7	13	13	26
0.75	0.7	12	12	24
0.7	0.7	11	11	22
0.6	0.7	10	10	20
0.9	0.6	21	21	42
0.8	0.6	17	17	34
0.75	0.6	16	16	32
0.7	0.6	15	15	30
0.6	0.6	13	13	26

Safety and tolerability: The following safety measures will be used:

- 1) Collection of vital signs
- 2) Collection of adverse events/side effects. All adverse events including minor rTMS side-effects like post-treatment headache as well as serious and unexpected adverse events like seizure will be recorded. All participants will be encouraged to call or page the PI if they notice any adverse effect or if they are concerned about any medical issues. Side effects will be monitored at each treatment and office visit.

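### Remission and CGI-I improvement: Boschloo's exact test would keep the 5% level and be more powerful than Fisher's at the planned remission rates (a cheap gain, not an error in the plan)

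*Combined protocol and SAP*

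**What the plan says.** All references are to the combined protocol and SAP.

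- **Test.** In section 6, under the statistical analysis for the primary objective, the random effects models come first. The plan then adds that remission (HAMD at most 7, or PHQ9 of zero) and improvement (CGI-I at most 2) rates "between the two groups will be calculated using Fischer's Exact test".
- **Level.** General Description, item d: "All statistical tests will be judged for significance based upon a two-sided p-value of less than 0.05".
- **Sample size.** Power Analysis: "Sample size was calculated with (StataCorp, Texas, 2009) alpha was set at 0.05". For the active arm, "we hypothesize improvement in symptoms on the HAMD of 60-70% in the experimental group"; for sham, "we hypothesize a remission rate of 10% in the Control group". Table 7 labels both as remission rates, 0.7 or 0.6 against 0.1. At 15 per arm it gives power 0.9 and 0.7 respectively. N=30 is chosen for feasibility, and the abstract plans 15 per arm.
- **Role.** The listed primary efficacy measures are changes in HAMD, PHQ9 and BSS. The comparisons of rates supplement their models.

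The documents neither discuss how conservative Fisher's test is at this size nor name an alternative.

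**The concern.** Fisher's test conditions on the total number of events. In a table this small few p-values are then possible, and the test cannot get close to 0.05. It therefore uses well under half of the error rate that the plan allows.

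Remission is the only outcome with a power calculation, and feasibility fixes N. The choice of test is thus one of the few ways left to gain power. It also has to be made in advance. A result of 8/15 against 2/15 has Fisher p = 0.0502 and Boschloo p = 0.023, and changing the test after seeing such a result would not be credible.

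**Working it through.** **Inputs.** Two-sided alpha 0.05 (General Description d); 15 per arm (Abstract); remission 0.6 or 0.7 against 0.1 (Power Analysis, Table 7).

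**Step 1: reproduce Table 7.** The usual two-proportion formula, with p̄ the mean of the two rates, is

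n = [z(0.975)·√(2p̄(1−p̄)) + z(power)·√(p1(1−p1)+p2(1−p2))]² / (p1−p2)²,

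and the continuity correction is n' = (n/4)·[1 + √(1 + 4/(n·|p1−p2|))]².

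- 0.7 vs 0.1, power 0.9: n = (1.960·0.6928 + 1.2816·0.5477)²/0.36 = 11.79, so n' = 14.93, rounded up to 15.
- 0.6 vs 0.1, power 0.7: n = (1.960·0.6745 + 0.5244·0.5745)²/0.25 = 10.54, so n' = 14.26, rounded up to 15.

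All ten rows reproduce this way. Without the correction these two rows would be 12 and 11. Table 7 therefore used the corrected formula, which approximates Fisher's test, so the planned test and the sample size agree.

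**Step 2: true size at 15 vs 15.** For a rejection region R, size(p) = Σ over (a,b) in R of Bin(a;15,p)·Bin(b;15,p), summed over the 16 × 16 possible results and maximised over p.

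- Fisher (p < 0.05): 0.0055 at p = 0.10, 0.0167 at 0.20, 0.0177 at 0.25, 0.0165 at 0.50. The maximum is 0.0177.
- Boschloo (orders tables by Fisher's p-value, then sets the cut-off so that the maximum size stays at or below 0.05): it rejects when Fisher's p is at most 0.0996. The maximum size is 0.0433.

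Fisher rejects 102 tables. Boschloo rejects those and 20 more, 122 in all. With 0, 1, 2, 3 or 4 sham remitters, Fisher needs 5, 7, 9, 10 or 11 active remitters, and Boschloo needs 4, 6, 8, 9 or 10.

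**Step 3: power.** This is the same sum, with Bin(a;n1,p1)·Bin(b;n2,0.1).

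| Active/sham | Fisher max size | 0.6 vs 0.1: Fisher → Boschloo | 0.7 vs 0.1: Fisher → Boschloo |
|---|---|---|---|
| 15/15 | 0.018 | 0.739 → 0.845 | 0.894 → 0.950 |
| 16/14 | 0.031 | 0.813 → 0.856 | 0.932 → 0.953 |
| 15/14 | 0.028 | 0.760 → 0.829 | 0.905 → 0.943 |
| 15/13 | 0.030 | 0.776 → 0.823 | 0.909 → 0.936 |
| 14/13 | 0.033 | 0.763 → 0.784 | 0.900 → 0.921 |
| 15/12 | 0.030 | 0.782 → 0.798 | 0.904 → 0.922 |
| 14/14 | 0.021 | 0.742 → 0.807 | 0.887 → 0.927 |
| 13/13 | 0.029 | 0.710 → 0.813 | 0.880 → 0.922 |
| 12/12 | 0.023 | 0.639 → 0.770 | 0.826 → 0.895 |

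At 15/15 the gains are 0.845 − 0.739 = 10.6 points and 0.950 − 0.894 = 5.6 points. In the unequal splits they run from about 2 to 7 points.

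**Step 4: what the gain is worth.** With equal arms at 0.6 vs 0.1, Fisher's power is 0.827 at 17 per arm and 0.862 at 18. It therefore needs 36 patients to match the 0.845 that Boschloo reaches with 30.

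**The case against.** **Nothing is broken.** Fisher's test is valid and standard at this size. Table 7 states 90% and 70%, and Fisher delivers 89.4% and 73.9%. This stands. A reader might infer from its low true size that the trial is underpowered or that the test is wrong; Table 7 contradicts the first, and the second does not follow.

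**The largest gain depends on equal arms.** Fifteen per arm is a target. Randomisation uses in-house software stratified on time since injury, no blocking is described, and the plan expects to track dropouts. In the unequal splits checked, Fisher's size is about 0.028 to 0.033 and the gain is about 2 to 7 points. This also stands, and it limits the claim. It does not reverse it, because Boschloo's rejection region contains Fisher's at any arm sizes.

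**CGI-I improvement.** The Power Analysis speaks of improvement in the active arm, so a reader might apply the power gain to the CGI-I comparison. That figure concerns the HAMD, and Table 7 treats it as remission. No CGI-I rates are planned. Only the size result carries over, because it depends on the arm sizes alone.

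**Role.** The comparisons of rates are supplementary in a pilot study. That lowers the priority, although the sample size rests on one of them.

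**Conclusion.** A cheap improvement is available; it is neither an error nor a shortfall from plan. At 15 vs 15 Fisher's true size is at most 0.018, and with modest imbalance or dropout about 0.02 to 0.033. For remission at the Table 7 rates, Boschloo's test adds 10.6 points (0.6 vs 0.1) or 5.6 points (0.7 vs 0.1) at 15 vs 15, and about 2 to 7 points if the arms are unequal, with the level still at or below 0.05.

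The power figures assume that the Table 7 rates hold, that patients are independent, and that the analysis is unstratified with a known outcome for every patient counted. They apply to remission only.

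It is also tempting to treat any less conservative test as equally safe. Mid-p is not: it carries no guarantee, and its maximum size is 0.054 at 16/14 and 0.062 at 15/14.

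**What to change.** In section 6, in the paragraph on remission and improvement rates under the primary objective, make three changes:

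1. Name Boschloo's exact test, two-sided 0.05, for remission and for CGI-I improvement.
2. Report the risk difference with its 95% confidence interval for each.
3. Keep Fisher's p-value as a sensitivity result.

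Do not substitute a mid-p test, stratified or not, because it does not guarantee the 5% level. Make the change before any unblinded data are seen.

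The cost is one line of text and a freely available routine. No patients are added and Table 7 can stay as it is. The small downside is that readers know the test less well, which the Fisher sensitivity result offsets.
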